3.2.5. Hospitalizations and Pulmonary Function Decline

The number of hospitalizations is summarized within each intervention arm as follows: (i) The proportion of participants with at least one hospitalization, (ii) The average number of hospitalizations per participant, (iii) The rate of hospitalizations per participant week of follow-up, and (iv) The number of days hospitalized per participant. Poisson regression modeling is used to

derive rate ratios and 95% confidence intervals. Rates by arm are compared using a two-sided 0.05 level test for Poisson count data. Proportions of participants with at least one hospitalization are also compared between arms with estimated differences and corresponding 95% confidence intervals by the Newcombe-Wilson method without continuity correction; p-values are from a two-sided 0.05 level Fisher's Exact test. The difference between intervention arms in participants hospitalized is estimated using logistic regression methods and reported with confidence intervals accounting for randomization strata.

The proportions of participants with a significant decline in FEV₁ % predicted from Week 0 are also summarized by intervention arm.

3.2.6. Analyses of Primary Endpoint

The primary endpoint is the difference between arms in the change in FEV₁ % predicted from Week 0 (Visit 1) to Week 6 (Visit 3). The primary analysis for non-inferiority is conducted on the per-protocol analysis (PPA) population. An ANOVA model is used to adjust for dichotomous randomization strata: Week 0 FEV₁ % predicted, treatment combination at screening, prior study enrollment, and Week 0 age. The estimated effect of discontinuation and corresponding 95% confidence interval are reported, and the p-value is evaluated for a one-sided alpha-level 0.025 test of non-inferiority with a margin of -3% absolute change in FEV₁ % predicted. An unadjusted estimate is also provided.

The primary analysis is repeated in the ITT population. Missing outcome data in the ITT population were imputed using the least favorable treatment mean in arms discontinuing treatment and the most favorable treatment mean in arms continuing treatment. In this case, the least (most) favorable treatment mean is defined as the mean of the arm with the greater negative (positive) change from Week 0 to Week 6. Complete case results, including participants based on availability of non-missing values, are also reported.

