3.2.9. Summary of CRISS and CFQ-R scores

Absolute changes in CRISS and CFQ-R, respiratory domain, from screening to Week 0 (Visit 1) and from Week 0 (Visit 1) to each post-randomization visit are summarized. Mean differences between intervention arms at each visit and corresponding 95% confidence intervals are presented. Changes from Week 0 (Visit 1) to Week 6 (Visit 3) are assessed using a two-sample, two-sided t-test. Additionally, the changes in CRISS and CFQ-R, respiratory domain, between intervention arms are compared between intervention arms using an ANOVA model adjusting for randomization strata.

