3.2.11. Summary of Lung Clearance Index (LCI)

Demographics and baseline characteristics of the subset participants with multiple breath washout procedure completed are summarized as described in Section 3.1.3. Absolute and relative change in Lung Clearance Index (LCI) from screening to Week 0 (Visit 1) and from Week 0 (Visit 1) to each post-randomization visit are summarized. Mean differences between intervention arms at each visit and corresponding 95% confidence intervals are presented. Changes from Week 0 (Visit 1) to Week 6 (Visit 3) are assessed using a two-sample, two-sided t-test. Additionally, the changes in LCI between intervention arms are compared between intervention arms using an ANOVA model adjusting for randomization strata.

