	STOP Taking Mean Estimate (N=)	KEEP Taking Mean Estimate (N=)	Difference Unadjusted (95% CI) [1]	Difference Adjusted for Randomization Strata (95% CI) [2]	Excess Harm Boundary [3]	Alpha Spending (proportion)
Planned Analyses						
	Interim 1 (n =)					
	Interim 2 (n =)					
Conducted Interims						
	Interim 1 (n =)					
	Interim 2 (n =)					

[1] 95% confidence interval calculated using two-sample t-test. The difference is STOP Taking – KEEP Taking.

[2] Adjusted for randomization strata: On both HS and DA (vs. **only DA at screening**, Age (≥18 vs. <18 years), Week 0 (Visit 1) FEV₁ % Predicted (≥90% vs. <90%), and prior study enrollment (yes vs. no).

[3] The boundary for harm is based on hypothesis tests evaluating whether the estimated difference between arms (STOP Taking – KEEP Taking) for the absolute change in FEV₁ (% predicted) is less than the pre-specified margin for harm (-1.5), assuming a common standard deviation of 8.4, a one-sided 0.025 alpha level, and a Pocock adjustment for group sequential monitoring at two planned analyses. Harm is detected if the point estimate for the adjusted difference is less than the corresponding Excess Harm Boundary.

Table 6.2. Sensitivity Analysis: Results from ANOVA Model for Change in FEV₁ (% Predicted) (ITT population; Final Report)

The primary endpoint, absolute change in FEV₁ (% predicted) from Week 0 (Visit 1) to Week 6 (Visit 3), is compared between intervention arms using Analysis of Variance adjusted for dichotomous randomization strata: Week 0 FEV₁% predicted, treatment combination at screening, prior study enrollment, and Week 0 age. An unadjusted estimate is also provided.

Model Covariates	STOP Taking Mean Estimate (N=)	KEEP Taking Mean Estimate (N=)	Δ FEV ₁ (% Predicted) Estimate (95% CI)	P-value [9]
Complete Case				
Model Unadjusted				
Intervention Arm:	STOP Taking hypertonic saline [1,2]			
Model Adjusted for Randomization Strata				
Intervention Arm:	STOP Taking hypertonic saline [2,3]			
Randomization Strata:	FEV ₁ % Predicted ≥90% [4] On both HS and Dnase [5] Prior study enrollment [6] Age ≥18 years [7]			
Imputed Week 6 FEV₁ (% predicted) [8]				
Model Unadjusted				
Intervention Arm:	STOP Taking hypertonic saline [1,2]			
Model Adjusted for Randomization Strata				
Intervention Arm:	STOP Taking hypertonic saline [2,3]			
Randomization Strata:	FEV ₁ % Predicted ≥90% [4] On both HS and Dnase [5] Prior study enrollment [6] Age ≥18 years [7]			

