The following table summarizes the estimate for the difference in the change in CRISS score between intervention arms from Week 0 (Visit 1) to Week 6 (Visit 3) using an Analysis of Variance model. The models summarized are for an unadjusted model and one that adjusts for the randomization strata: Week 0 FEV₁ % Predicted (≥90% or <90%), therapy combination at screening (single or concurrent use of hypertonic saline and/or dornase alfa), prior study enrollment (yes or no), and Week 0 age (≥18 years or < 18 years).

Model Covariates	STOP Taking Mean Estimate	KEEP Taking Mean Estimate	Difference (95% CI)	P-value [9]
Per Protocol Analysis Population	(N=)	(N=)		
Model Unadjusted				
Intervention Arm:	STOP Taking hypertonic saline [1, 2]			
Model Adjusted for Randomization Strata				
Intervention Arm:	STOP Taking hypertonic saline [2, 3]			
Randomization Strata:	FEV ₁ % Predicted ≥90% [4] On both HS and Dnase [5] Prior study enrollment [6] Age ≥18 years [7]			
Intent to Treat Population [8]	(N=)	(N=)		
Model Unadjusted				
Intervention Arm:	STOP Taking hypertonic saline [1, 2]			
Model Adjusted for Randomization Strata				
Intervention Arm:	STOP Taking hypertonic saline [2, 3]			
Randomization Strata:	FEV ₁ % Predicted ≥90% [4] On both HS and Dnase [5] Prior study enrollment [6] Age ≥18 years [7]			

[1] The overall unadjusted intervention arm difference (STOP Taking - KEEP Taking) is estimated using a twosample t-test.

[2] Compared to reference level, KEEP taking hypertonic saline.

[3] Least Squares Mean Estimates from model with weighting proportional to observed frequencies of randomization factor combinations in the data.

[4] Compared to reference level, FEV₁ % Predicted < 90% at Week 0 (Visit 1).

[5] Compared to reference level, one therapy at Week -2 (Screening).

[6] Compared to reference level, no prior study enrollment.

[7] Compared to reference level, age <18 years at Week 0 (Visit 1).

[8] Missing values are imputed using the least favorable treatment mean in arms discontinuing treatment and using most favorable treatment mean in arms continuing treatment.
[9] Two-sided p-value.

Figure 9.2. Change in CFQ-R Respiratory Domain Scaled Score over Time (PPA and ITT population for Final Report)

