	N (%)		
	Mean (SD)		
	Median		
	Min, Max		
Difference in Absolute Changes (Week 0 to Week 2 minus Week -2 to Week 0)			
	N (%)		
	Mean (SD)		
	Median		
	Min, Max		
Week 6 (Visit 3)			
	N (%)		
	Mean (SD)		
	Median		
	Min, Max		
Absolute Change (Week 0 to Week 6)			

Visit		STOP Taking (N=)	KEEP Taking (N=)	Difference (95% CI); P-value [1]
	N			
	Mean (SD)			
	Median			
	Min, Max			

[1] 95% confidence interval and p-value are calculated using a two-sample t-test. The difference is STOP Taking – KEEP Taking.

Table 9.4. Results from ANOVA Model for Change in CFQ-R Respiratory Domain Scaled Score (PPA and ITT population for Final Report)

The following table summarizes the estimate for the difference in the change in CFQ-R respiratory domain scaled score (%) between intervention arms from Week 0 (Visit 1) to Week 6 (Visit 3) using an Analysis of Variance model. The models summarized are for an unadjusted model and one that adjusts for the randomization strata: Week 0 FEV₁ % Predicted (≥90% or <90%), therapy combination at screening (single or concurrent use of hypertonic saline and/or dornase alfa), prior study enrollment (yes or no), and Week 0 age (≥18 years or < 18 years).

Model Covariates	STOP Taking Mean Estimate (N=)	KEEP Taking Mean Estimate (N=)	Difference (95% CI)	P-value [9]
Per Protocol Analysis Population				
Model Unadjusted				
Intervention Arm:	STOP Taking hypertonic saline [1, 2]			
Model Adjusted for Randomization Strata				
Intervention Arm:	STOP Taking hypertonic saline [2, 3]			
Randomization Strata:	FEV ₁ % Predicted ≥90% [4] On both HS and Dnase [5] Prior study enrollment [6] Age ≥18 years [7]			
Intent to Treat Population [8]				
Model Unadjusted				
Intervention Arm:	STOP Taking hypertonic saline [1, 2]			
Model Adjusted for Randomization Strata				
Intervention Arm:	STOP Taking hypertonic saline [2, 3]			
Randomization Strata:	FEV ₁ % Predicted ≥90% [4] On both HS and Dnase [5] Prior study enrollment [6] Age ≥18 years [7]			

[1] The overall unadjusted intervention arm difference (STOP Taking - KEEP Taking) is estimated using a twosample t-test.

[2] Compared to reference level, KEEP taking hypertonic saline.

[3] Least Squares Mean Estimates from model with weighting proportional to observed frequencies of randomization factor combinations in the data.

[4] Compared to reference level, FEV₁ % Predicted < 90% at Week 0 (Visit 1).

[5] Compared to reference level, one therapy at Week -2 (Screening).

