	N (%)		
	Mean (SD)		
	Median		
	Min, Max		
Week 6 (Visit 3)			
	N (%)		
	Mean (SD)		
	Median		
	Min, Max		
Absolute Change (Week 0 to Week 6)			

Visit		STOP Taking (N=)	KEEP Taking (N=)	Difference (95% CI); P-value [1]
	N			
	Mean (SD)			
	Median			
	Min, Max			

[1] 95% confidence interval and p-value are calculated using a two-sample t-test. The difference is STOP Taking – KEEP Taking.

Table 9.6. Results from ANOVA Model for Change in Treatment Burden Scaled Score (PPA and ITT population for Final Report)

The following table summarizes the estimate for the difference in the change in CFQ-R treatment burden domain scaled score (%) between intervention arms from Week 0 (Visit 1) to Week 6 (Visit 3) using an Analysis of Variance model. The models summarized are for an unadjusted model and one that adjusts for the randomization strata: Week 0 FEV₁ % Predicted (≥90% or <90%), therapy combination at screening (single or concurrent use of hypertonic saline and/or dornase alfa), prior study enrollment (yes or no), and Week 0 age (≥18 years or < 18 years). Only participants with a Week 0 CFQ-R treatment burden domain scaled score are included in this model.

Model Covariates	STOP Taking Mean Estimate (N=)	KEEP Taking Mean Estimate (N=)	Difference (95% CI)	P-value [9]
Per Protocol Analysis Population				
Model Unadjusted				
Intervention Arm:	STOP Taking hypertonic saline [1, 2]			
Model Adjusted for Randomization Strata				
Intervention Arm:	STOP Taking hypertonic saline [2, 3]			
Randomization Strata:	FEV ₁ % Predicted ≥90% [4] On both HS and Dnase [5] Prior study enrollment [6] Age ≥18 years [7]			
Intent to Treat Population [8]				
Model Unadjusted				
Intervention Arm:	STOP Taking hypertonic saline [1, 2]			
Model Adjusted for Randomization Strata				
Intervention Arm:	STOP Taking hypertonic saline [2, 3]			
Randomization Strata:	FEV ₁ % Predicted ≥90% [4] On both HS and Dnase [5] Prior study enrollment [6] Age ≥18 years [7]			

[1] The overall unadjusted intervention arm difference (STOP Taking - KEEP Taking) is estimated using a twosample t-test.

[2] Compared to reference level, KEEP taking hypertonic saline.

[3] Least Squares Mean Estimates from model with weighting proportional to observed frequencies of randomization factor combinations in the data.

[4] Compared to reference level, FEV₁ % Predicted < 90% at Week 0 (Visit 1).

[5] Compared to reference level, one therapy at Week -2 (Screening).

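### The models for change in FEV1, CRISS, CFQ-R and LCI adjust only for four binary strata; adding the continuous baselines already collected costs almost nothing and usually gains some precision

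*SAP*

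**What the plan says.** SAP 3.2.6 sets out the primary model: "An ANOVA model is used to adjust for dichotomous randomization strata". The four factors are Week 0 FEV1 (split at 90% predicted), treatment combination at screening, prior study enrollment, and age (split at 18). Table 6.2, the ITT repeat, uses the same form: change is "compared between intervention arms using Analysis of Variance adjusted for dichotomous randomization strata".

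The secondary outcomes follow suit. SAP 3.2.9 says that "changes in CRISS and CFQ-R, respiratory domain, between intervention arms are compared between intervention arms using an ANOVA model adjusting for randomization strata", and SAP 3.2.11 says that "the changes in LCI between intervention arms are compared between intervention arms using an ANOVA model adjusting for randomization strata". The shells for Tables 9.2 (CRISS), 9.4 (CFQ-R respiratory), 9.6 (CFQ-R treatment burden) and 11.3 (LCI) list arm and the same four factors. None has a term for the outcome's own baseline. Protocol 14.2 and 14.3 likewise name only the randomization strata.

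The continuous values exist. Protocol Appendix 2 schedules spirometry, CRISS and CFQ-R at both Screening and Visit 1, and the SAP tabulates them (Tables 7.1, 9.1, 9.3 and 9.5). Table 11.3 defines a single LCI baseline, Week 0 or else Screening, and excludes participants without one. Table 9.6 also requires a baseline: "Only participants with a Week 0 CFQ-R treatment burden domain scaled score are included in this model".

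**The concern.** A change score is usually negatively correlated with its own baseline. In a 1:1 randomized comparison of this size, adding that baseline to a linear model cannot raise the asymptotic variance of the arm difference and usually lowers it. The plan uses a coarse split of the baseline for FEV1 and no baseline at all for CRISS, CFQ-R and LCI. Two of the models already require a baseline value for entry and then leave it out.

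What is at stake is interval width, not validity. Protocol 14.7 gives 74% power if stopping truly costs 0.5 points, so even a small gain on the primary test is useful. LCI matters because it is a secondary objective measured only at selected sites. Protocol 6.1 expects up to 400 subjects with MBW data across the protocol, or about 200 per study if evenly divided.

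**Working it through.** **1. The plan's own power.** Inputs from Protocol 14.7 and SAP 3.2.6: 308 subjects (154 per arm), SD of change 8.4, margin -3, one-sided alpha 0.025, no covariates.

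- SE = 8.4 × √(2/154) = 0.957.
- True difference 0: Φ(3/0.957 − 1.96) = 0.880; noncentral t gives 0.878. The protocol states 88%.
- True difference -0.5: Φ(2.5/0.957 − 1.96) = 0.743; noncentral t gives 0.740. The protocol states 74%.

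Both figures reproduce.

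**2. Cost of a useless covariate.** One residual degree of freedom adds about 0.3% to the variance at 308 subjects and about 0.5% at 200.

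**3. FEV1.** The documents give neither a baseline SD nor a between-visit correlation, so these are assumed. Screening, Week 0 and Week 6 FEV1 were drawn as trivariate normal (600,000 draws) with mean 92 and SD 12 to 20 before selection. Draws were kept if Screening was at least 60 and the run-in fall was under 10 points, as eligibility requires. The correlation was tuned so that the change has SD 8.4. Change was regressed on (a) the 90% split, (b) that plus continuous Week 0, and (c) that plus Screening. With correlation decaying from visit to visit (Markov), at n = 308:

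| SD | Variance cut, (b) vs (a) | Power, true 0 | Power, true -0.5 | CI half-width |
|---|---|---|---|---|
| 12 | 4.7% | .901 → .914 | .772 → .791 | 1.813 → 1.770 |
| 14 | 3.3% | .894 → .904 | .763 → .776 | 1.833 → 1.803 |
| 16 | 2.4% | .890 → .897 | .757 → .767 | 1.846 → 1.824 |
| 18 | 1.8% | .887 → .893 | .753 → .760 | 1.855 → 1.839 |
| 20 | 1.4% | .885 → .889 | .750 → .756 | 1.862 → 1.849 |

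Adding Screening (c) gives nothing further under Markov decay. The total cut becomes 5.4 to 7.7% if the Screening–Week 6 correlation lies midway between ρ and ρ², and about 17% only if all visits are equally correlated.

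A separate simulation of 6,000 trials per setting, without the eligibility cuts, gave mean SE reductions of 2.3, 1.4, 0.9 and 0.4% at SD 12, 15, 18 and 25. The SE was smaller in 99, 94, 86 and 66% of trials, so a narrower interval is likely but not certain in any one trial.

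**4. CRISS, CFQ-R and LCI.** Let ρ be the Week 0–Week 6 correlation and k the ratio of Week 6 SD to Week 0 SD. Ignoring what the strata explain, the share of the change variance explained by the baseline is

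(1 − ρk)² / (1 + k² − 2ρk),

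which at k = 1 reduces to (1 − ρ)/2: 25, 15, 10 and 5% for ρ = 0.5, 0.7, 0.8 and 0.9. The interval narrows by 1 − √(1 − share):

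| k | ρ = 0.5 | 0.7 | 0.8 | 0.9 |
|---|---|---|---|---|
| 0.9 | 18.3% | 13.3% | 11.2% | 10.0% |
| 1.0 | 13.4% | 7.8% | 5.1% | 2.5% |
| 1.1 | 9.6% | 4.0% | 1.6% | 0.0% |
| 1.25 | 5.5% | 1.0% | 0.0% | 2.5% |

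At k = 1 and ρ = 0.7, a 15% variance cut is worth 1/0.85 − 1 = 17.6% more subjects.

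**5. A Screening term for CRISS and CFQ-R.** Take k = 1 and ρ = 0.7, so the change variance is 0.6 in units of the baseline variance. Week 0 alone cuts 15%. If the Screening–Week 6 correlation is midway, (0.7 + 0.49)/2 = 0.595, the two baselines explain 0.512 of Week 6 variance and the cut is 1 − 0.488/0.6 = 18.6%. With equal correlation they explain 0.576 and the cut is 29.4%. Under Markov decay there is no further gain.

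**6. Imputed ITT models.** With n = 400, k = 1 and 12% of changes imputed by the SAP 2.4 rule (12% is the loss allowed for in SAP 1.2), the model-based variance cut over 3,000 trials is 22, 13 and 4% at ρ = 0.5, 0.7 and 0.9. With nothing missing it is 25, 15 and 5%. Imputed changes are unrelated to baseline, which dilutes the gain. If 5% of Week 0 scores were also missing (an assumption), about 20 of 400 subjects would drop out of an adjusted model. Filling those with the pooled mean keeps them and leaves the cut about the same.

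**The case against.** The strongest objection is that nothing is wrong. Adjusting for the stratification factors is standard, both documents agree on it, and Protocol 14.7 describes its power calculation as conservative because it leaves covariates out. On the primary endpoint the gain is a few hundredths of a point in half-width against a margin of 3, because the 90% split already carries about 60 to 64% of the baseline variance under normality. All of this stands, and it limits the point to efficiency.

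A second objection concerns the primary population. The PPA set is selected after randomization on diary completion, adherence, antibiotic use and Week 6 FEV1, so neither a 1:1 split nor baseline balance is guaranteed there. With Week 0 slopes of about -0.25 to -0.09, a 1-point imbalance within FEV1 strata would move the estimate by 0.09 to 0.25 points, more than the precision gained. That is correct. However, the strata-only model relies on comparable arms in the same set, so adjusting for an observed baseline difference does no harm. Nor does it cure selection on post-randomization behavior.

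A third objection is that the secondary gains rest on assumed ρ and k, and that no secondary endpoint carries a power target. Also true; hence the ranges, which include zero. On timing, the SAP changes were signed in August 2022, and the interim harm rule uses the strata-adjusted estimate: "Harm is detected if the point estimate for the adjusted difference is less than the corresponding Excess Harm Boundary". This is a reason to leave the interim table alone and to fall back on a supportive analysis where the primary model is settled.

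**Conclusion.** The point holds as an improvement in efficiency, not a correction of an error. For the primary test the gain from continuous Week 0 FEV1 is small: 0.4 to 1.3 power points at a true difference of 0, 0.6 to 1.9 points at -0.5, and 0.01 to 0.04 points off a half-width of 1.81 to 1.86. Anything larger depends on how Screening, Week 0 and Week 6 FEV1 correlate. CRISS, CFQ-R and LCI may gain more, with intervals up to 13.4% narrower at equal SDs and ρ = 0.5, but the gain shrinks, possibly to zero, when the Week 6 SD exceeds the Week 0 SD. Every size rests on assumed SDs and correlations, because the documents give none; the secondary figures also ignore what the strata already explain. The statement about four strata concerns the main cohorts of Studies A and B; the lower lung function cohort adjusts for one factor only (SAP 3.2.13).

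**What to change.** In SAP 3.2.6, 3.2.9 and 3.2.11, and in Tables 6.1.a, 6.2, 9.2, 9.4, 9.6 and 11.3:

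- Keep arm and the four strata factors, and add the continuous baseline of the same outcome: the Week 0 value or, for LCI, the single baseline already defined.
- Add the continuous Screening value as well for FEV1, CRISS and both CFQ-R domains.
- Fill a missing Screening or Week 0 covariate with the mean pooled over arms, so that no subject leaves the planned analysis set. This matters most for the imputed ITT models in Tables 9.2 and 9.4, whose shells state no Week 0 requirement. Keep the existing entry restrictions of Tables 9.6 and 11.3.
- Leave interim Table 6.1.b as planned. Do not carry the Week 0 covariate into the run-in model of Table 7.4, where Week 0 is part of the outcome.
- If the primary model is already fixed, or aggregate results are known, report the adjusted model as a supportive analysis beside the strata-only one.

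The cost is SAP wording, one or two extra model terms per table and the corresponding degrees of freedom. No new data or visits are needed, and Protocol 14.1 allows the SAP to carry changes to the analysis plan.

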11 DISCONTINUATION AND REPLACEMENT OF SUBJECTS

11.1 Early Withdrawal of Subjects from a Study

All subjects are free to withdraw from participation at any time, for any reason, specified or unspecified, and without prejudice.

Reasonable attempts will be made by the investigator to provide a reason for early subject withdrawals. The reason for the subject's early withdrawal from the study will be specified in the subject's source documents. Subjects who withdraw early from the study (prior to Visit 3) should be encouraged to come in for a final early study withdrawal visit (and the procedures to be followed would include those at Visit 3).

Subjects who for any reason modify their hypertonic saline or dornase alfa treatment such that it deviates from their assigned treatment regimen within a study will not be withdrawn from the study and are encouraged to complete all scheduled study visits.

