2.4 Definition of the Analysis Populations

Enrollment and screening summaries will be generated using all screened participants. All participant disposition, secondary, exploratory, and safety summaries will be performed using an intent to treat (ITT) population, defined as all participants randomized at Visit 1 (Day 0). The primary analyses in both Study A and Study B will be performed using a per-protocol analysis (PPA) population, as defined below. Sensitivity analyses, repeating the primary analyses, will be done on the ITT population. Secondary analyses will likewise be run on the PPA population and repeated on the ITT population.

PPA is defined by the following criteria:

1. Daily diary completion ("Compliance") from Week 0 (Visit 1) to Week 6 (Visit 3)
 - a. $\geq 70\%$ non-missing data
 - b. $\geq 70\%$ non-missing in last 2 weeks

2. Daily diary responses from Week 0 (Visit 1) to Week 6 (Visit 3) aligned with randomized treatment (“Adherence”)
 - a. to assigned treatment regimen (HS or Dnase) among non-missing days overall (>=70%)
 - b. to assigned treatment regimen (HS or Dnase) among non-missing days in 2 weeks (>=70%)
3. No initiation of new acute oral, inhaled, or IV antibiotics for respiratory symptoms (rate from ETI trial was ~5%) from Week 0 (Visit 1) to Week 6 (Visit 3)
4. Non-missing FEV at Week 6 (Visit 3)
5. Given the correct randomization instructions
6. Minimum 70% use of ETI among non-missing days in last 2 weeks
7. Eligible at Week -2 (Screening Visit) and at Week 0 (Visit 1, Randomization)

Data from subject disposition visits will be allocated to the nearest subsequently scheduled visit. Missing outcome data in the ITT population for the final primary analysis and for key secondary analyses (CRISS, CFQ-R, and LCI) will be imputed using the least favorable treatment mean in arms discontinuing treatment and using the most favorable treatment mean in arms continuing treatment. Complete case results, including participants based on availability of non-missing values, will also be reported.

3. Overview of Planned Analyses

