[1] The overall unadjusted intervention arm difference (STOP Taking - KEEP Taking) is estimated using a two sample t-test.

[2] Compared to reference level, KEEP taking **hypertonic saline**.

[3] Least Squares Mean Estimates from regression model with weighting proportional to observed frequencies of randomization factor combinations in the data.

[4] Compared to reference level, FEV₁ % Predicted < 90% at Week 0 (Visit 1).

[5] Compared to reference level, one therapy at Week -2 (Screening).

[6] Compared to reference level, no prior study enrollment.

[7] Compared to reference level, age <18 years at Week 0 (Visit 1).

[8] Missing values are imputed using the least favorable treatment mean in arms discontinuing treatment and using most favorable treatment mean in arms continuing treatment.

[9] One-sided test for non-inferiority

Figure 6.1.a. Observed Treatment Effect Confidence Intervals in Relation to Non-inferiority Margin (Primary Analysis: PPA population; Sensitivity Analysis: ITT population; Final Report)

This figure displays the observed treatment effect along with corresponding 2-sided 95% confidence intervals. The dashed line at $x=\Delta$ indicates the non-inferiority margin; the tinted region indicates the zone of inferiority. Panel (a) shows results for PP population (unadjusted and adjusted for covariates) and panel (b) show results for ITT population (unadjusted and adjusted for covariates).

[1] Missing values are imputed using the least favorable treatment mean in arms discontinuing treatment and using most favorable treatment mean in arms continuing treatment. (Final report ITT)

Figure 6.1.b. Interim Analysis Boundary for Excess Harm (Interim Report)

This figure displays the observed treatment effect adjusted for randomization strata and corresponding 2-sided 95% confidence interval. The gray region indicates the zone of Excess Harm with interim boundaries. The boundaries for harm are based on hypothesis tests evaluating whether the estimated difference between arms (STOP Taking – KEEP Taking) for the absolute change in FEV₁ (% predicted) is significantly less than the Excess Harm Margin of -1.5 (dashed line), assuming a common standard deviation of 8.4, a one-sided 0.025 alpha level, and a Pocock adjustment for group sequential monitoring at two planned analyses. The statistical criteria for detecting Excess Harm is met if the observed treatment effect estimate falls within the gray region.

7 Summary of Spirometry Results

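### The ITT imputation analyses one fixed mean per arm as if observed: no penalty when STOP looks worse, an interval that is too narrow, and no clear statement of what is imputed

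*SAP*

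**What the plan says.** SAP 2.4 states that missing ITT data for the primary endpoint and for CRISS, CFQ-R and LCI are "imputed using the least favorable treatment mean in arms discontinuing treatment and using the most favorable treatment mean in arms continuing treatment". Section 3.2.6 repeats the rule for FEV1 and adds that "the least (most) favorable treatment mean is defined as the mean of the arm with the greater negative (positive) change from Week 0". The filled-in data then go through the same strata-adjusted ANOVA and the same one-sided 0.025 test against -3. Neither section mentions multiple imputation, a bootstrap or any other variance correction.

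The text selects the arm by its change but does not say whether the mean filled in is the mean change or the mean Week 6 value. The Table 6.2 shell labels the block "Imputed Week 6 FEV₁ (% predicted", and its footnote only repeats the rule.

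Other provisions limit the reach of the rule:
- The per-protocol population requires "Non-missing FEV at Week 6 (Visit 3", so the primary analysis has nothing to impute.
- SAP 2.4 adds: "Complete case results, including participants based on availability of non-missing values, will also be reported".
- Protocol 11.1 says "Subjects who withdraw early from the study (prior to Visit 3) should be encouraged to come in for a final early study withdrawal visit", and SAP 2.4 says "Data from subject disposition visits will be allocated to the nearest subsequently scheduled visit". Both reduce missing Week 6 data.

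The footnote to Figure 6.1.a ties the plotted ITT result to the imputed version: "using most favorable treatment mean in arms continuing treatment. (Final report ITT".

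**The concern.** The rule is built to be conservative: the worse mean for those who stop, the better mean for those who continue. But the two means are ranked by the observed result. If STOP has the worse observed change, STOP's unfavorable mean is its own and KEEP's favorable mean is its own. The rule then applies no penalty in the only situation that threatens non-inferiority. It pulls STOP down only when STOP is observed better, where the result is already clear of the margin.

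The imputed constants also count as real observations, so the reported precision is overstated.

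The ITT analysis is the declared check on a per-protocol primary analysis that removes people for non-adherence, acute antibiotics or missing Week 6 FEV1. A check that cannot worsen the estimate when STOP is worse, and that two programmers could implement differently, does not do that job.

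**Working it through.** **Inputs.** SD of change 8.4, margin -3, one-sided 0.025 (Protocol 14.2 and 14.7); about 200 per arm (Protocol 6.1). The documents give no missing-FEV1 rate. SAP 1.2 allows 12% loss to follow-up for interim planning. Protocol 14.7 gives a 20% ceiling that also covers non-adherence. With withdrawal visits, 12% is likely too high; 3-5% is our assumption. Missingness is taken as random and equal by arm.

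**Plan's own figure.** With 154 per arm, SE = 8.4 × √(2/154) = 0.957. Power at no effect = Φ(3/0.957 - 1.96) = 88%; at -0.5, Φ(2.5/0.957 - 1.96) = 74%. Both match Protocol 14.7.

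**Change score imputed, STOP observed worse.** Let m be the missing fraction. The unadjusted estimate equals complete case. Complete-case SE = 8.4√(2/200)/√(1-m) = 0.84/√(1-m). Filling in a constant adds count but no spread, so the reported SE is about 0.84√(1-m). The ratio is (1-m), and error at -3 is 1 - Φ(1.96(1-m)). Simulation is strata-adjusted, 40,000 trials per cell.

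| m | SE complete case | SE imputed | Error, formula | Error, simulated | Coverage at -3, simulated |
|---|---|---|---|---|---|
| 3% | 0.85 | 0.83 | 2.9% | 2.9% | 94.3% |
| 5% | 0.86 | 0.82 | 3.1% | 3.2% | 93.8% |
| 12% | 0.90 | 0.79 | 4.2% | 4.2% | 91.7% |
| 20% | 0.94 | 0.75 | 5.8% | 5.8% | 88.3% |

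Simulated complete-case error was 2.4-2.6% throughout. At a true difference of 0 with 12% missing, overall coverage is 94.4%.

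**STOP observed better by d.** The imputed difference is (1-m)d - md = (1-2m)d. The complete-case lower limit is then already above -1.96 × 0.94 = -1.84, even at 20% missing, so the penalty falls where it cannot matter.

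**Direction.** Over 12 cells (true -3, -1.5, -0.5, 0; m = 3%, 5%, 12%) and 480,000 trials, 13,316 complete-case fails became passes and 10 passes became fails. The count depends on the cells chosen; the direction is the point.

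**Week 6 value imputed.** STOP still receives its own mean when worse, but each imputed change now carries the person's baseline deviation. With baseline SD b, uncorrelated with change, the nominal variance per arm is ((1-m)8.4² + m·b²)/n and the true variance is (8.4² + m·b²)/(n(1-m)). At m = 12%, b = 15: nominal SE = √(2 × (62.1 + 27)/200) = 0.94; true SE = √(2 × (70.6 + 27)/176) = 1.05; error = 1 - Φ(1.96 × 0.94/1.05) ≈ 4.0%. For b = 10 and 20 the formula gives 4.1% and 3.8%. Simulation over b = 10-20 and baseline-change correlation 0 to -0.3 gives 2.9-4.4% at 12%, 2.8-3.2% at 5% and 2.6-3.0% at 3%. The simulated SE at 12% is 0.86, 0.94 and 1.04 for b = 10, 15, 20, against 0.90 for complete case.

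**Non-inferiority pass rates**

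| Truth, m | Complete case | Change imputed | Week 6 value, b = 10 / 15 / 20 |
|---|---|---|---|
| 0, 12% | 91% | 95% | 91 / 86 / 79% |
| -0.5, 12% | 79% | 85% | 79 / 72 / 65% |
| 0, 5% | 93% | 94% | 93 / 90 / 88% |

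With b = 15 and 12% missing, the two readings reach opposite conclusions in 10%, 16% and 20% of trials at true 0, -0.5 and -1.5. At 5% missing they disagree in 5% at true 0 and 13% at -1.5.

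**Secondary endpoints (two-sided, change imputed, no true effect).** Harm is declared in 3.2% and benefit in 2.0% at 5% missing; 4.4% and 1.2% at 12%. Nominal is 2.5% each. The tilt here is towards declaring harm.

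**The case against.** The strongest reply is that nothing decisive rests on this analysis. It is a sensitivity analysis, and Table 6.2 places complete case beside it, unadjusted and adjusted, so any narrowing is visible. At a realistic 5% missing the half-width is 1.61 against 1.69, a shift of 0.08 point in the lower limit. All of that stands, and it limits the weight of the point.

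A second reply is that only a block label supports the Week 6 reading: the analysed endpoint is the change, and the label could mean baseline plus mean change, which is the change reading. That is a fair interpretation, but the SAP does not state it. The baseline SD, mean and correlation are indeed assumptions. With an assumed normal baseline of mean 90, SD 20 would put about 7% below the adult entry floor of 60, so the top of that range is the least plausible.

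Third, the secondary tables also carry adjusted per-protocol estimates without imputation, and Tables 9.1, 9.3, 9.5 and 11.2 give unadjusted ITT differences with no imputation specified. That is true. Still, the ITT blocks of Tables 9.2, 9.4, 9.6 and 11.3 hold imputed results only, so no shell contains the adjusted complete-case ITT estimate.

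Finally, a smaller repair exists: keep the arm-selection rule and add Rubin's variance. At 12% missing that gives 2.3% error and 95.6% coverage at -3. It corrects the interval but still applies no stress when STOP is worse.

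**Conclusion.** The concern holds and should be fixed; it does not touch the primary conclusion. As written, the imputed ITT interval is too narrow when STOP is worse, under either reading. Only the change reading makes the test consistently easier to pass than complete case. Under the Week 6 reading, error at -3 is mildly inflated, yet at baseline SD 15-20 the test is harder to pass near no effect. The practical size is modest at 3-5% missing and material at 12%. Withdrawal visits reduce missingness but do not remove it: data move to the nearest later visit, so someone who withdraws before Week 2 still lacks a Week 6 value. These sizes rest on random, equal missingness, the planned SD of 8.4 and, for the Week 6 reading, an assumed baseline distribution.

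**What to change.** - In SAP 2.4, 3.2.6 and the Table 6.2 label, state that the Week 0 to Week 6 change is the imputed quantity.
- Replace the single-mean rule with multiple imputation by arm, combined by Rubin's rules, using the strata and available earlier visits as predictors. LCI has no Week 2 value, because the washout test is not scheduled then.
- For FEV1, add a tipping-point table that shifts imputed STOP values only, from 0 to -3 points. For CRISS, CFQ-R and LCI use the same imputation; delta tables are optional.
- Add the promised complete-case rows to Tables 9.2, 9.4, 9.6 and 11.3, and show complete case in Figure 6.1.a.
- If the signed rule is kept for the record, report it as supplementary, name the imputed quantity, and state which direction is unfavorable for CRISS and LCI; the definition in 3.2.6 covers FEV1 only.
- Log the change in the SAP change table, marked post hoc if data have been seen.

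A check with 20 imputations and an assumed correlation of 0.5 between Week 2 and Week 6 change gave error 2.4% and coverage 95.2% at 12% missing, and 2.1% and 95.4% at 5%. With no true effect and the full -3 shift, the estimate moves to -0.37 with an 84% pass rate at 12%, and to -0.14 with 92% at 5%.

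The cost is SAP wording and some programming; no new data are needed. Against the change reading, the half-width grows from about 1.61 to 1.69 at 5% missing and from 1.55 to 1.75 at 12%. The no-effect ITT pass rate at 12% falls from about 95% to 91%.
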